**Emicizumab—F. Hoffmann-La Roche Ltd**

Protocol MO40865, Version 2.0

ACTIVE SUBSTANCE:	Emicizumab
PRODUCT REFERENCE NUMBER:	EMA/H/C/004406
PROCEDURE NUMBER:	NA
JOINT PASS	No
RESEARCH QUESTION AND OBJECTIVES:	
The main aim of this study is to assess the safety of emicizumab use in children with hemophilia A in real world conditions, among pediatric patients enrolled in the PedNet Registry.
 
The primary objective for this study is as follows:
 
 
• To evaluate the overall safety and tolerability of emicizumab administration, in all patients and in subgroups determined by age and status of inhibitor as well as by severity for patients without inhibitors
 
 
Primary safety endpoints:  Frequency and incidence of thromboembolic events (TE), thrombotic microangiopathy (TMA), and anaphylaxis
 
The secondary objectives for this study are as follows:
 
 
• To evaluate frequency and incidence of any adverse events reported to the PedNet Registry in patients treated with emicizumab, overall and in subgroups determined by age and status of inhibitor as well as by severity for patients without inhibitors
 
 
Secondary safety endpoints:
 
 
○ Any AEs reported to PedNet Registry
 
 
 
• To describe the bleeding profile of patients treated with emicizumab, overall and in subgroups determined by age and status of inhibitor as well as by severity for patients without inhibitors
 
 
Effectiveness endpoints:

	
 
○ Annual bleeding rate (ABR) for treated* bleeds and percentage of patients with zero treated bleeds
 
○ ABR for joint bleeds and major bleeds
 
○ Bleeds count for soft tissue bleeds and minor bleeds
 
 
*As per PedNET data collection, all bleeds reported are treated bleeds

COUNTRIES OF STUDY POPULATION:	
Countries with hemophilia centers participating in the PEDNET registry:
 
Austria, Belgium, Canada, Czech Republic, Denmark, Finland, France, Germany, Greece, Ireland, Israel, Italy, Norway, Portugal, Spain, Sweden, Switzerland, The Netherlands, and United Kingdom

### LIST OF TABLES

Table 1	Possible Sample Sizes .....	22
---------	-----------------------------	----

1. **LIST OF ABBREVIATIONS**

Abbreviation	Definition
ABR	Annual Bleeding Rate
AE	Adverse Event
BPA	Bypassing Agents
eCRF	Electronic Case Report Form
FVIII	Blood Coagulation Factor VIII
HTC	Hemophilia Treatment Center
MAH	Marketing Authorization Holder
NI	Non-interventional
PASS	Post-Authorization Safety Study
PedNet	Pediatric Network on haemophilia management
PRAC	Pharmacovigilance Risk Assessment Committee
PT	Preferred term
Q1W	Once a week
SAE	Serious Adverse Event
TE	Thromboembolic Event
TMA	Thrombotic Microangiopathy

### 3. ABSTRACT/SYNOPSIS

**TITLE:** EMICIZUMAB USE IN PEDIATRIC PATIENTS IN THE REAL WORLD: AN ANALYSIS OF THE PEDNET REGISTRY

**PROTOCOL NUMBER:** MO40685

**VERSION NUMBER:** 2.0

**DATE OF SYNOPSIS:** 16 May 2023

**EU PAS REGISTER NUMBER:** EUPAS31954

**STUDIED MEDICINAL PRODUCT:** Emicizumab, Hemlibra®

**SCIENTIFIC RESPONSIBLE:** [REDACTED], F.Hoffmann-La Roche AG

**MAIN AUTHOR:** [REDACTED], F.Hoffmann-La Roche AG

**PHASE:** IV, non-interventional study

**INDICATION:** Hemophilia A

**MARKETING AUTHORIZATION HOLDER:** Roche Registration GmbH  
[name],  
[name],  
Germany

#### RATIONALE AND BACKGROUND

Hemophilia A is an X-linked recessive bleeding disorder characterized by deficiency or absence of blood coagulation factor VIII (FVIII), which leads to a lifelong bleeding tendency.

Primary prophylaxis has proven to minimize bleeding events and complications and has become standard-of-care among pediatric patients.

Although effective when optimally administered, prophylaxis with intravenous (IV) FVIII infusion can be accompanied by significant burden of treatment with impact on the quality of life of both patients and their caregivers. Furthermore, the development of neutralizing antibodies (inhibitors) against FVIII occurs in up to 30% of patients after exposure to therapeutic FVIII concentrates.

Emicizumab (also known as Hemlibra®) is a humanized monoclonal modified immunoglobulin G4 antibody that bridges activated factor IX (FIX) and factor X to restore the function of missing activated FVIII needed for effective hemostasis. Given that emicizumab has no structural relationship to FVIII, its efficacy is not affected by the presence of FVIII inhibitors and is not expected to induce or enhance the development of inhibitors to FVIII or to other coagulation factors. Emicizumab has been evaluated in many clinical trials and approved by multiple countries.

Two important risks have been identified with the use of activated prothrombin complex

concentrate (aPCC) in patients treated with emicizumab prophylaxis: TEs and TMA. Thromboembolic events not associated with concomitant use of aPCC has been identified as an important potential risk. In addition, anaphylaxis, anaphylactoid, or systemic hypersensitivity reactions were considered as potential safety risks based on the class of biological drugs.

While the results observed in the clinical trials supporting the benefit-risk assessment at the time of the marketing authorization application are compelling and demonstrate a favorable benefit-risk profile, experience with emicizumab in the pediatric population has been primarily based on pediatric patients with inhibitors. In addition, there is no clinical experience with emicizumab use in newborns (birth to Day 28 of life), who are vulnerable to development of severe bleeds. The post-approval evaluation of the drug's outcomes and utilization is vital to assessing whether the efficacy and safety profile observed in clinical trials match the real-world experience in all age groups. To address this, data collected by the Pediatric Network on haemophilia management (PedNet) Registry is extracted and analyzed according to the current protocol, and Annual Reports is generated.

### **Research Question and Objectives**

The main aim of this study is to assess the safety of emicizumab in real world conditions, among pediatric patients with hemophilia A enrolled in the PedNet Registry.

The primary objective for this study is as follows:

- To evaluate the overall safety and tolerability of emicizumab administration, in all patients and in subgroups determined by age and status of inhibitor as well as by severity for patients without inhibitors.
  - Primary safety endpoints: Frequency and incidence of TEs, TMA, anaphylaxis

The secondary objectives for this study are as follows:

- To evaluate frequency and incidence of any adverse events reported to the PedNet Registry in patients treated with emicizumab, overall and in subgroups determined by age and status of inhibitor as well as by severity for patients without inhibitors.
  - Secondary safety endpoints: Any AEs reported to PedNet Registry
- To describe the bleeding profile of patients treated with emicizumab, overall and in subgroups determined by age and status of inhibitor as well as by severity for patients without inhibitors
  - Effectiveness endpoints: ABR for treated\* bleeds and percentage of patients with zero treated bleeds
  - ABR for joint bleeds and for major bleeds.
  - Bleeds count for soft tissue bleeds and minor bleeds

\* As per PedNET data collection, all bleeds reported are treated bleeds

### **STUDY DESIGN**

This is a non-interventional, secondary data use Post-Authorization Safety Study (PASS) relying on data collected as part of the PedNet Registry.

PedNet is a multicenter, observational research database that includes patients with FVIII/IX levels  $\leq 0.025$  IU/mL born after 1 January 2000 and treated in one of the participating Hemophilia Treatment Centers (HTCs).

### **DATA SOURCES**

PedNet is a collaboration of 32 pediatric HTCs in 19 countries (EU and Canada), providing an infrastructure for clinical research and management of children with hemophilia. The PedNet Registry started in 2003 and collects real-life data from all newly diagnosed children born with hemophilia and treated at the participating centers. Data is collected through well-defined web-based Case Report Forms using a secure data entry system capturing all aspects of hemophilia from birth to adolescence and adulthood. The database is hosted at the University Medical Center Utrecht in the Netherlands. Centers are visited regularly for on-site data monitoring with frequency according to their size with audit of baseline information (all data entered) and bleed and medication information (10%–50% of the data entered). Data on inhibitor results are all checked and interpreted centrally. In addition to monitoring of source data, numerous pre-specified logical checks are performed on the dataset. All inconsistencies or suspected errors are resolved by queries to the centers. All centers have obtained approval of their local ethical committee according to local regulations. Prior to inclusion into the Registry signed informed consent is obtained from the parents. If required by local regulations, additional consent is obtained from patients after reaching 12 years of age included in the Registry.

### **POPULATION**

The following criteria describe the population eligible for this study, which is a subset of the overall population participating in the PedNet Registry.

Inclusion criteria for inclusion in the PedNet Registry:

- Diagnosis of hemophilia A
- Factor VIII activity < 25 IU/dL
- Treated in one of the participating centers

Additional inclusion for emicizumab-specific analysis:

- Received prophylactic treatment with emicizumab

Exclusion criteria for the PedNet Registry:

- Referral to a participating HTC after development of inhibitors
- Informed consent for participation in the PedNet Registry not obtained

Exclusion criteria for emicizumab-specific analysis:

- Inherited or acquired bleeding disorder other than hemophilia A

### **VARIABLES**

#### **PRIMARY SAFETY VARIABLES**

The primary variables for this study are as follows:

- TE, TMA events, anaphylaxis (including terms of systemic hypersensitivity, anaphylaxis, and anaphylactoid events)

#### **SECONDARY VARIABLES**

The secondary variables for this study are as follows:

- Other AEs reported to the registry including new inhibitor development, unexpected poor efficacy, etc. Unexpected poor efficacy is included in “Other” category of AE collection in the PedNet Registry electronic case report forms (eCRF).
- Bleeding event (yes/no)
- Bleed location (joint bleed, soft tissue bleed), severity (major versus minor\*)
  - \*Note: Per PedNet protocol definition:
    - Major bleed: bleed characterized by pain, swelling, limitation of motion and failure to respond within 24 hours of treatment
    - Minor bleed*: bleed characterized by minor pain, minimal swelling, minimal restriction of motion, resolving within 24 hours of treatment
    - Joint bleed: any complaint requiring treatment located in a joint
    - Soft tissue bleed*: any complaint requiring treatment located outside the joints
- Concomitant administration of coagulation factor concentrate products (type and dose of product (FVIII product, aPCC, rFVIIa)) in patients receiving emicizumab.

### **STUDY SIZE**

The sample size depends on the approval and uptake of emicizumab in the countries with centers participating in the PedNet Registry. As of January 2019, PedNet enrolled 1795 patients with hemophilia A, of which 1173 patients had severe disease, 225 patients had moderate disease and 397 patients had mild disease. Of the patients with severe disease, 351 patients had inhibitor diagnosed between 2000 and 2019.

Assuming a constant sample size of patients with severe disease in the registry (N=1173 with severe disease regardless of FVIII inhibitor and N=351 with inhibitor), and assuming that at least 50% of these patients receive emicizumab during the 6 years of the study, the anticipated sample size is expected to be n=587 for patients with severe disease and n=176 for patients with inhibitor at the end of this 6-year study.

No data about inhibitor status is available at this stage for patients with moderate disease. Assuming a constant sample size of patients with moderate disease in the registry (N=225 with moderate disease regardless of FVIII inhibitor), and assuming that at least 15% of these patients receive emicizumab during the 6 years of the study, the anticipated sample size is expected to be n=34 for patients with moderate disease.

The MAH acknowledges that these estimates may change if the total number of patients enrolled in the registry changes significantly during the study time.

### **DATA ANALYSIS**

General principles for data analysis are provided below.

Safety analyses will be conducted in all patients overall and in subgroups defined by age and status of inhibitor as well as by severity for patients without inhibitors, using all authorized emicizumab dosing regimens. Proportions of patients developing each type of AE (e.g., TE, TMA, and anaphylaxis) are calculated along with the corresponding 95% CIs, and are reported for all patients as well as in age-defined subgroups including newborns with or without inhibitors.

Bleed outcomes analyses will be conducted in all patients overall and in subgroups defined by age and status of inhibitor as well as by severity for patients without inhibitors. Mean ABR with standard deviation and percentage of patients with zero bleeds are reported overall and in subgroups defined by age and status of inhibitor as well as by severity for patients without inhibitors. Summary statistics are provided overall and for the relevant subgroups.

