Emicizumab (also known as Hemlibra®) is a humanized monoclonal modified immunoglobulin G4 antibody with a bispecific antibody structure. Given that emicizumab has no structural relationship to FVIII, its efficacy is not affected by the presence of FVIII inhibitors and is not expected to induce or enhance the development of inhibitors to FVIII or to other coagulation factors. Emicizumab clinical development program included the following studies enrolling children or adolescents: Study BH29992 (HAVEN 2) in 85 patients <12 years of age and 3 adolescent patients (aged 12–18 years of age) with inhibitors, as well as inclusion of adolescent patients as part of Study BH29884 (HAVEN 1; 32 patients with inhibitor, once a week [Q1W] dosing regimen), Study BH30071 (HAVEN 3; 8 patients without inhibitors, Q1W or every 2 weeks dosing regimen), Study BO39182 (HAVEN 4; 1 patient with inhibitors and 3 patients without inhibitors, every 4 weeks dosing regimen), Study BO41423 (HAVEN6) included patients with mild or moderate hemophilia A without inhibitors (16 patients <12 years of age and 14 adolescent patients aged 12–18 years of age), in addition, Study MO41787 (HAVEN7) recruited 55 patients from birth to ≤ 12 months of age with severe hemophilia A without FVIII inhibitors. At the time of developing this protocol, emicizumab is approved in approximately 114 countries worldwide in patients with hemophilia A with FVIII inhibitors and is approved in approximately 102 countries worldwide for the expanded indication to include patients with hemophilia A without FVIII inhibitors, including approval in the US, Japan, and the EU. In European Union, emicizumab was approved for routine prophylaxis in adult and pediatric patients with severe hemophilia A (congenital factor VIII deficiency) without inhibitor on 11 March 2019. At the time of protocol amendment, emicizumab was also approved for routine prophylaxis in patients with moderate hemophilia A (congenital factor VIII deficiency) without inhibitor with severe bleeding phenotype (European Commission Decision received on 23 January 2023). This approval was based on study BO41423 (HAVEN 6; including 51 patients with moderate disease, receiving emicizumab loading dose 3 mg/kg SC Q1W for 4 weeks followed by a maintenance dose of either 1.5 mg/kg SC QW, 3 mg/kg SC Q2W or 6 mg/kg SC Q4W based on patient preference) ([Négrier et al. 2023](#)).

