PedNet emicizumab specific report includes patients who are treated with emicizumab. The following data includes in the reports: number of patients treated with emicizumab, duration of emicizumab exposure, number of TE, TMA, anaphylaxis, and any other AEs,

ABR for treated bleeds, percentage of zero bleeds, ABR for joint bleeds, ABR for soft tissue bleeds, ABR for major or minor bleeds, number of patients which have used bypassing aPCC agents when treated with emicizumab, number of patients which have used FVIII products when treated with emicizumab, the number of patients used rFVII when treated with emicizumab and detailed data for patients who have developed TE, TMA or and anaphylaxis. Based on the PedNet annual report, the MAH produces the PASS report annually with the following information grouped by age and status of inhibitor as well as by severity for patients without inhibitors and/or include the results in the annual PBRRER depending on the time of availability of PedNet reports:

- Number of patients exposed to emicizumab (directly from PedNet report)
- Number of patients exposed to emicizumab who experienced TE, TMA, and anaphylaxis (calculated from PedNet report)
- Proportion and incidence of each AE of TE, TMA, and anaphylaxis among patients receiving emicizumab (calculated based on information from PedNet report)
- Number of patients exposed to emicizumab and each of the following drugs: aPCC, rFVIIa, FVIII (directly from PedNet report)
- Number of patients exposed to emicizumab and each of the following drugs: aPCC, rFVIIa, FVIII, who experienced TE, TMA, and anaphylaxis (calculated from PedNet report)
- Proportion of TE and of TMA among patients exposed to emicizumab and each of the following drugs: aPCC, rFVIIa, and FVIII (calculated based on information from PedNet report)
- Number of any other AE and number of patients with any other AE (including inhibitor development, unexpected poor efficacy, local subcutaneous reactions) reported to PedNet Registry (directly from PedNet report)
- ABR for treated bleeds, percentage of zero bleeds, ABR for joint bleeds and ABR for major bleeds (directly from PedNet report)
- Bleeds count for soft tissue bleeds and minor bleeds

PedNet performs annual data extractions in January of each year. Following each data extraction, PedNet group analyzes the data according to this protocol and provide the MAH with Annual Emicizumab-Specific Reports.

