## 8.7 DATA ANALYSIS

### Data transformation

The MAH will receive aggregate level data of patients treated with emicizumab from the PedNet Registry on an annual basis.

Based on the number of patients, number of AEs, and exposure to emicizumab provided by the Registry, the MAH will perform analyses of frequencies/incidence of AEs overall and grouped by age and status of inhibitor as well as by severity for patients without inhibitors. The youngest age group will be newborn (birth to 28days). Other age groups include: 29 days-<6 months, 6 months-<2 years, 2 years-<6 years, 6 years-<12 years, 12 years-18 years. The MAH will report ABR for treated bleeds, percentages of zero bleeds, ABR for joint bleeds and major bleeds overall and grouped by age and status of inhibitor as well as by severity for patients without inhibitors as sent by PedNet registry. ABRs for soft tissue bleeds and minor bleeds is not calculated by PedNet and therefore only the number of bleeds will be presented.

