### 8.7.1 Primary Analyses

The primary AEs are TE, TMA, and anaphylaxis. Additional AEs including inhibitor development and unexpected poor efficacy will be included as they are collected by PedNet Registry.

Adverse events collected in PedNet are not collected according to MedDRA classification. Most events are collected according to pre-specified lists; however, free-text fields are also available for each event. Whenever possible, AEs will be reclassified by Roche according to MedDRA PT level using the most current MedDRA version.

Primary analyses: For each AE of interest (TMA, TE, and anaphylaxis), the following analysis will be performed overall and grouped by age and status of inhibitor as well as by severity for patients without inhibitors:

- Annual incidence rate of the AE among patients exposed to emicizumab will be estimated as the number of patients who were treated with emicizumab and developed the AE, divided by the person years of emicizumab exposure. The numerator will be calculated using report from PedNet.
- PedNet will provide number of patients treated with emicizumab and emicizumab mean exposure days, which will be used to calculate the person years of emicizumab exposure using the following formula:

Person years of emicizumab exposure=[number of patients exposed to emicizumab×mean emicizumab exposure time in days–number of patient exposed to emicizumab and had event×(mean emicizumab exposure time in days/2\*)]/365.25

\*Note that this calculation accounts for patients who are censored in the study once they have experienced an adverse event (event is imputed to happen after half the exposure time).

Exact binomial 95% confidence intervals will be calculated for each incidence rate.

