### **8.7.2            Secondary analyses:**

- Annual incidence proportion of AE of interest (TMA, TE, and anaphylaxis) among patients exposed to emicizumab will be estimated as the number of patients who were treated with emicizumab and developed the AE, divided by the number of patients who are exposed to emicizumab. The incidence proportion will be calculated overall and by age and status of inhibitor as well as by severity for patients without inhibitors.
- For each AE of interest (TMA, TE, and anaphylaxis), the following proportions will be calculated, together with the corresponding 95% confidence intervals:
  - Annual incidence proportions of the AE among patients treated with emicizumab and concurrently with each of the following drugs: aPCC, rFVIIa, and FVIII product.
- Annual number and percentage of each of the other adverse events reported to PedNet will be presented. Currently, in addition to TE, TMA, and anaphylaxis, these events may include: new inhibitors, allergic reactions, local subcutaneous reaction, other AEs including unexpected poor efficacy.
- ABRs: Estimates for the ABR are based on a negative-binomial model adjusted for age group and inhibitor status. The negative-binomial models each use the “total number of bleeds” (for each specified type of bleed) as the outcome and the model is offset by the “total duration of follow-up” since first exposure to emicizumab.

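### Three secondary descriptive measures (zero-bleed percentage, annual AE proportion, soft tissue and minor bleed counts) have no time basis, so they vary with follow-up even when risk is equal

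*Protocol*

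**What the plan says.** Three secondary outputs are specified without a time basis.

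- **Zero bleeds.** This is a named effectiveness endpoint (Section 7.2). The Synopsis, Data Analysis, says that the "percentage of patients with zero bleeds are reported overall and in subgroups defined by age and status of inhibitor", and the sentence continues to severity for patients without inhibitors. Section 8.7 repeats the measure. None of these places gives a window or a minimum follow-up.
- **Annual incidence proportion.** Section 8.7.2 defines it for TE, TMA and anaphylaxis as the patients who "developed the AE, divided by the number of patients who are exposed to emicizumab".
- **Soft tissue and minor bleeds.** Section 8.7 states: "ABRs for soft tissue bleeds and minor bleeds is not calculated by PedNet and therefore only the number of bleeds will be presented". Section 8.1, listing what the PedNet report contains, includes "ABR for soft tissue bleeds, ABR for major or minor bleeds". The second list in Section 8.1, for the MAH's own report, has counts only.

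Two other outputs do use time. The primary AE incidence rate (Section 8.7.1) is "divided by the person years of emicizumab exposure", and the ABR model (Section 8.7.2) has a follow-up offset. Duration of exposure is a separate report item in Section 8.1, but no rule links it to the three measures above.

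**The concern.** Patients enter when they start emicizumab and are observed to a common cutoff, so follow-up is unequal. At a constant bleeding rate, the share with no bleed falls as follow-up lengthens, and the share with an AE and the bleed count both rise. Subgroups with different follow-up will therefore show different figures even when their risk is the same.

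The contrast most exposed is severe versus moderate disease without inhibitors. Section 4 gives reporting of safety in moderate patients without inhibitors as the reason for adding severity strata. Section 6 dates EU approval for severe patients without inhibitor to 11 March 2019 and for moderate patients to 2023 ("European Commission Decision received on 23 January 2023"). Data run to the end of 2024. Moderate patients could look better on zero bleeds and on AE proportion only because they were watched for less time.

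The word *annual* adds a second problem. If it means one-year risk, the formula does not deliver it. If it means recalculated each year, it labels what appears to be a cumulative figure: Section 8.5 describes the last interim report as counting all starters up to a cutoff of 31 December 2021.

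**Working it through.** **Inputs from the Protocol.** Approval dates (Section 6). End of data collection, taken as 31 December 2024 (Section 4). Anticipated sizes (Section 8.5).

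**Assumptions, not in the Protocol.** Same true bleed and AE rates in both groups, starts spread uniformly from approval to cutoff, no stopping. Bleed rate, dispersion k and AE rate are varied.

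**1. The plan's own figures.** 1173 × 0.50 = 586.5 (stated 587); 351 × 0.50 = 175.5 (176); 225 × 0.15 = 33.75 (34). All reproduce. The Protocol gives no expected zero-bleed or AE proportion to check.

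**2. Maximum on-label follow-up T.** Severe: 2122 days / 365.25 = 5.81 years. Moderate: 708 / 365.25 = 1.94 years. Ratio 3.0.

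**3. Zero-bleed percentage.** With follow-up uniform on 0 to T and rate r:
- Poisson: (1 − e^(−rT)) / (rT)
- Negative binomial, k = 1: ln(1 + rT) / (rT)

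At r = 0.5, rT is 2.905 (severe) and 0.969 (moderate).
- Poisson: (1 − 0.055) / 2.905 = 32.5%; (1 − 0.379) / 0.969 = 64.0%
- k = 1: ln(3.905) / 2.905 = 46.9%; ln(1.969) / 0.969 = 69.9%

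Range, severe versus moderate (%):

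| Bleeds per year | Poisson | k = 1 | k = 2 |
|---|---|---|---|
| 0.1 | 75.8 v 90.9 | 78.8 v 91.4 | 81.0 v 91.8 |
| 0.25 | 52.7 v 79.3 | 61.8 v 81.5 | 67.2 v 83.2 |
| 0.5 | 32.5 v 64.0 | 46.9 v 69.9 | 55.4 v 73.7 |
| 1 | 17.2 v 44.2 | 33.0 v 55.6 | 43.9 v 62.3 |
| 2 | 8.6 v 25.3 | 21.8 v 40.9 | 33.8 v 50.5 |

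The gap runs from about 11 points (0.1, k = 2) to about 32 (0.5, Poisson). On a fixed 12-month window at 0.5 bleeds per year, both groups give 60.7% (Poisson) or 66.7% (k = 1).

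**4. AE proportion.** Expected value: 1 − (1 − e^(−λT)) / (λT). At λ = 0.01 per person-year it is 2.85% (severe) and 0.96% (moderate), against a true one-year risk of 1.0% in both. For λ from 0.002 to 0.02 the ratio stays at 2.9 to 3.0.

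The Section 8.7.1 person-year formula, with mean exposure set to T/2, handles the same situation correctly. The 587 includes patients with inhibitor, but n cancels.
- Severe: 16.8 events / (587 × 2.905 − 16.8 × 1.452 = 1681) = 0.0100
- Moderate: 0.33 / (34 × 0.969 − 0.33 × 0.485 = 32.8) = 0.0100

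**5. Bleed counts.** At 0.5 per year, bleeds per patient are 0.5 × 2.905 = 1.45 (severe) and 0.5 × 0.969 = 0.48 (moderate). Dividing by mean time returns 0.5 in both.

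**6. Sections 8.1 and 8.7.** One says that the PedNet report contains ABRs for soft tissue and minor bleeds. The other says that PedNet does not calculate them. Both cannot be right.

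**The case against.** The main measures already adjust for time, exposure duration is reported, and no subgroup test is planned. A reader who looks at the AE rate and the ABR will not be misled. This stands: the defect is confined to secondary descriptive figures, and a reader who inferred that the primary safety result is distorted would be wrong.

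A zero-bleed window could sit in an analysis plan that is not shown. That is fair for this one measure. It does not cover the proportion formula, the count-only rule or the conflict between Sections 8.1 and 8.7, all of which are fixed in the Protocol.

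A reader might infer that the approval dates force the difference in follow-up. The Protocol does not support that. Inclusion (Section 8.2) requires only prophylactic emicizumab, with no on-label or start-date condition. Section 8.5 assumes that moderate patients start at any time in the six years. Participating countries include some outside the EU. Actual follow-up by subgroup is nowhere stated. Nor does the argument extend to inhibitor status, since no approval date for that indication is given. For age, a separate cause exists: collection runs until age 18 (Section 8.1), which shortens follow-up for late starters.

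Placing every patient at maximum follow-up would give 6% versus 38% zero bleeds (Poisson, 0.5 per year). That is an extreme and not an expected result.

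The AE difference would hardly be visible. About 0.33 events are expected in 34 moderate patients at 1 per 100 person-years, and the exact upper 95% limit for 0/34 is 1 − 0.025^(1/34), about 10%.

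**Conclusion.** The point holds for three secondary measures and should be corrected. The AE proportion as defined is a crude cumulative proportion, so *annual* is wrong or at best misleading. The zero-bleed percentage has no common window. The soft tissue and minor bleed counts have no denominator, and the Protocol contradicts itself on whether their rates exist.

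The practical weight falls on zero bleeds, where equal bleeding could appear as a gap of tens of percentage points between severe and moderate patients without inhibitors. That size rests on assumed equal rates, uniform uptake from approval and assumed dispersion. Earlier starts in moderate patients would shrink it. The direction needs only that moderate patients are followed for less time, which is likely but not documented.

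**What to change.** - **Zero bleeds:** ask PedNet for the Kaplan-Meier percentage bleed-free at 12 months on emicizumab, by subgroup. The alternative, zero bleeds in the first 12 months among patients observed for 12 months, is simpler but drops everyone with shorter follow-up.
- **AE proportion:** report 12-month cumulative incidence, or keep the formula, rename it *crude cumulative proportion* and print exposure duration beside it for each subgroup.
- **Soft tissue and minor bleeds:** divide each count by person-years, formed as number of patients × mean exposure days / 365.25 from the quantities that PedNet already supplies under Section 8.7.1. The deduction there for patients with an event should not be applied, because bleeds recur and patients stay under observation.
- **Text:** reconcile Sections 8.1 and 8.7 on which ABRs PedNet provides.

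The cost is some extra registry output from data already held; the relabelling and the bleed rates need little or none. The 12-month figures must be requested in advance, because the MAH receives only aggregate results (Sections 8.3 and 8.7) and cannot rebuild them later.
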